### 8.2.4 Compatibility

Ipilimumab injection may be diluted in 0.9% Sodium Chloride Injection, United States Pharmacopeia (USP) or 5% Dextrose Injection.

### 8.2.5 Availability

Ipilimumab will be supplied as an investigational agent by Bristol-Myers Squibb (BMS).

### 8.2.6 Preparation

Ipilimumab injection (5 mg/mL) can be used for intravenous (IV) administration after transferring to a polyvinyl chloride (PVC), non-PVC/non-di-(2-ethylhexyl)phthalate (DEHP), or glass container and is stable for 24 hours at 2°C to 8°C or room temperature/room light (RT/RL). Ipilimumab injection may be diluted in 0.9% Sodium Chloride Injection, United States Pharmacopeia (USP) or 5% Dextrose Injection. Preparation will follow institutional standard. The product may be infused using a volumetric pump at the protocol-specific dose(s) and rate(s) through a infusion set with an inline, sterile, nonpyrogenic, low-protein-binding filter (pore size of 0.2 to 1.2 micrometer).

Ipilimumab injection must not be administered as an IV push or bolus injection. Care must be taken to assure sterility of the prepared solutions since the drug product does not contain any antimicrobial preservatives or bacteriostatic agents.

### 8.2.7 Administration

Ipilimumab will be administered as an IV infusion over approximately 60 minutes ( $\pm$  5 minute infusion window). Ipilimumab will be administered every 6 weeks, on cycle day 1. Calculation of weight should be done per institutional standards of practice. Re-calculation of dosage for fluctuations in body weight should be made in accordance with institutional guidelines. On days where both nivolumab and ipilimumab will be administered, nivolumab should be administered first. The ipilimumab infusion will start at least 30 minutes after completion of the nivolumab infusion.

### 8.2.8 Ordering

Ipilimumab will be ordered by site pharmacy personnel from BMS. Each participating institution is responsible for completing the applicable drug supply forms to receive re-supply of Ipilimumab for the the duration of the study. Except in very unusual circumstances, each participating institution will order the study agent(s). A participating site may order the agent(s) only after the initial IRB approval for the site has been forwarded by the Coordinatin Center to the supplier.

### 8.2.9 Accountability

The investigator, or a responsible party designated by the investigator, should maintain a careful record of the inventory and disposition of the agent using the NCI Drug Accountability Record Form (DARF) or another comparable drug accountability form. (See the NCI Investigator's Handbook for Procedures for Drug Accountability and Storage.)

#### 8.2.10 Destruction and Return

Expired or unused supplies of ipilimumab should be destroyed according to institutional policies. Destruction will be documented in the Drug Accountability Record Form.

### 9. BIOMARKER, CORRELATIVE, AND SPECIAL STUDIES

In all patients in whom a tumor safely accessible, two biopsies will be required: baseline biopsy and on-treatment biopsy and at day 29 of cycle 1 (+14 day scheduling window). Optional biopsies will be performed at progression in patients who experienced an objective response during the study. We plan to use baseline biopsy tissue to perform a number of immune profiling assays, detailed below. On baseline tumor biopsies, we will perform characterization based on histology (TILs), protein expression, and mRNA expression. Additionally, we will bank specimens for possible future DNA analysis, and other further testing.

All participants will be asked to provide a sample of their archival tissue. For participants in whom tumor biopsies are not safely accessible, an archival sample will be required in order to enroll. In these cases, teams should ensure that an archival sample is available, but it does not need to be at the site in order for the patient to start treatment. Though listed as a screening procedure, archival tissue may be requested and obtained at any point throughout the trial.

Serial blood draws for correlative science are required on this trial; blood samples will be collected within 7 days before starting therapy; blood draws will be obtained every 6 weeks for 24 weeks, and then every 12 weeks, at the end-of-treatment visit in patients who are removed from treatment for progressive disease, and all efforts will be made to obtain an additional blood draw at the time of progressive disease, in patients who went off treatment for anything other than progressive disease. On each blood draw, we will perform flow cytometry to characterize protein expression of immune mediators, detailed below, and additional blood will be banked for future testing.

All patients will additionally be asked to provide a stool sample at three timepoints: within 14 days prior to starting treatment, during treatment at day 29 Cycle 1 (+14 day scheduling window), and at the end of treatment. A fourth collection may be requested from patients who experience grade  $\geq 2$  diarrhea related to study treatment after discussion with the PI. This collection is not required, but is strongly encouraged. These samples will be analyzed for microbiota content.

Sites may refer to the separate laboratory manual for additional correlative details including collection, processing, and shipping instructions.

Please note that some of the downstream correlative plans for blood and tissue include whole exome and single cell sequencing, plus analysis of the data generated, that will be performed by Foundation Medicine, Nanostring Technologies, and the Broad Institute of MIT.. All samples will be sent in a completely de-identified fashion and staff involved at the Broad Institute, Foundation Medicine, and Nanostring Technologies will not have any access to patient health information (PHI). The Broad Institute will provide barcode labels for all samples that are generated at random by their laboratory software.

## Summary of Specimens

Research Sampling	Timepoint	Contents	Destination
Archival Tissue	Anytime on study	1 FFPE Block or 10-20 5 micron unstained slides	Current DFCI CRC
Fresh Tissue	Baseline* (within 28 days of C1D1, prior to treatment start)	5-7 cores	RNAlater Cores – Breast Bank
	C1D29 (+14 day scheduling window)	5-7 cores	Formalin Cores – Breast Bank
	End of Treatment (Optional)	5-7 cores	External Sites Only: OCT Core – Breast Bank
Blood	Baseline*, Restaging Visits, Time of Progression	1 – 10mL Streck Tube (cfDNA)	Breast Bank
		5 – 10mL CPT tubes (PBMCs)*	Mayer 308 / [name]
Stool	Baseline*	Home Collection Kit (DNA Genotek)	Breast Tumor Immunology Lab/ [name], PhD
	At C1D29 (any time between C1D29 and C2D1)		
	End of treatment		
	Optional collection at the time of grade $\geq 2$ diarrhea		

Note: The “Breast Bank” and Core Blood and Tissue Bank are the same lab and interchangeable

\*Baseline samples preferably completed after registration or on Cycle 1 Day 1 prior to treatment start (once a study ID is assigned). Baseline samples completed during screening will not be a violation.

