#### 4.3 General Guidelines for Other Investigative Sites

Eligible participants will be entered on study centrally at the coordinating center through the Study Coordinator or Project Manager. The list of required forms can be found in section 4.4. Following registration, participants should begin protocol therapy within 7 days. Issues that would cause treatment delays should be discussed with the Overall PI. If the subject does not receive protocol therapy following registration, the subject must be taken off-study in the CTMS (OnCore) with an appropriate date and reason entered.

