### 9.2.2 Collection

Biopsies will be performed at the below timepoints, if tumor is safely accessible.

Mandatory:

- Baseline (preferably after registration or on Cycle 1 Day 1 prior to dosing):
- Around C1D29 (Any time from C1D29-C2D1 is allowed)

Optional:

- At time of progression or end of treatment

For patients proceeding to the retreatment phase, optional biopsies will be performed at the below timepoints:

- C1D1 of retreatment, prior to dosing
- At the time of progression after retreatment with nivolumab

Biopsies should not be performed on Friday afternoons, as there may not be time for processing of the fresh tissue. If a biopsy must be performed on Friday morning, the lab of [name] and [name] must be notified ahead of time to ensure that there will be adequate time for processing fresh tissue, since fresh tissue cannot be stored over the weekend. The specimens in RNALater, OCT, and formalin may be stored over the weekend and shipped on Monday. Specimens in RNA Later and formalin should be stored at room temperature until shipment.

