- j. Tumor assessments should consist of 1) CT and/or MRI of the chest/abdomen/pelvis, 3) any other imaging studies (CT neck, plain films, etc.) as clinically indicated by the treating physician. The same radiographic procedures and technique must be used throughout the study for each patient (e.g., if the patient had CT chest/abdomen/pelvis performed during screening, then she should subsequently undergo CT performed using the same radiologic protocol throughout the remainder of the study). Tumor assessments will be performed at baseline, at day 1 ( $\pm 7$  day scheduling window) of Cycles 2, 3, and 4 and then every 12 week [ at day 1 ( $\pm 7$  day scheduling window) of every odd cycle: C6, C8, C10, etc.]. Additional scans are permitted as clinically indicated. All known sites of disease documented at screening should be re-assessed at each subsequent tumor evaluation.
- k. For those taken off the study for reasons other than progressive disease, tumor measurements should continue to be repeated every 6-12 weeks until first disease progression or start of a new anti-cancer therapy. Every effort should be made to maintain this scheduled, but it is understood that it may not be possible in all cases. Failure to complete scans at this interval will not be deemed protocol violations.
- l. Collected at screening, every restaging, end of treatment (if removed for progressive disease) and optionally at time of progression. See section 9.0
- m. Baseline tumor biopsy should be obtained within 28 days prior to initiating protocol therapy. On treatment biopsies should be obtained at C1D29 (+14 day scheduling window). A tumor biopsy may be performed at the end of treatment. See Section 9.2.
- n. Archival tumor sample should be collected (block or if not possible, 10-20 5micron, unstained positively charged slides). This sample may be collected at any time throughout the lifetime of the study.
- o. Baseline stool collection should be obtained within 14 days before starting protocol therapy. On treatment stool collection should be obtained at C1D29 (anytime from C1D29-C2D1). A stool collection should be obtained at the end of treatment. As these collections are for exploratory correlative purposes, failure to provide a sample at these timepoints will not constitute a protocol violation. See section 9 and/or lab manual for stool collection and processing instructions.

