## **2.3 Participating Institution**

Each Participating Institution is expected to comply with all applicable federal regulations and DF/HCC requirements, the protocol and HIPAA requirements.

The general responsibilities for each Participating Institution may include but are not limited to:

- Document the delegation of research specific activities to study personnel.
- Commit to the accrual of participants to the protocol.
- Submit protocol and/or amendments to their local IRB.
- Maintain regulatory files as per sponsor requirements.
- Provide the Coordinating Center with regulatory documents or source documents as requested.
- Participate in protocol training prior to enrolling participants and throughout the trial as required (i.e. teleconferences).
- Update Coordinating Center with research staff changes on a timely basis.
- Register participants through the Coordinating Center prior to beginning research related activities.
- Submit Serious Adverse Event (SAE) reports to local IRB per institutional requirements and to the Coordinating Center, in accordance with DF/HCC requirements.

- Submit protocol deviations and violations to local IRB per institutional requirements and to the DF/HCC Sponsor in accordance with DF/HCC requirements.
- Order, store and dispense investigational agents and/or other protocol mandated drugs per federal guidelines and protocol requirements.
- Have office space, office equipment, and internet access that meet HIPAA standards.
- Participate in any quality assurance activities and meet with monitors or auditors at the conclusion of a visit to review findings.
- Promptly provide follow-up and/or corrective action plans for any monitoring queries or audit findings.

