### 3.7.2 Initiation of Therapy

Participants must be registered with the DF/HCC CTMS before the initiation of treatment or other protocol-specific interventions. Treatment and other protocol-specific interventions may not be initiated until the Participating Institution receives confirmation of the participant's registration from the Coordinating Center. The DF/HCC Sponsor and DFCI IRB must be notified of any violations to this policy.

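### For external sites, Section 9 and the calendar allow the baseline research biopsy during screening, while Appendix E 3.7.2 bars it until registration is confirmed

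*Combined protocol and SAP*

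**What the plan says.** **Where the biopsy is allowed during screening.** In the Section 9 Summary of Specimens, an asterisk on the baseline entries for fresh tissue, blood and stool leads to a two-part footnote. The first part is a preference: "Baseline samples preferably completed after registration or on Cycle 1 Day 1 prior to treatment start (once a study ID is assigned"). The second is a permission: "Baseline samples completed during screening will not be a violation". Section 9.2.2 makes the baseline biopsy mandatory where the tumor is safely accessible, and again only prefers the later timing. The Section 10 calendar marks the research biopsy in the Screening column, and its footnote m counts back from treatment, not from registration: "Baseline tumor biopsy should be obtained within 28 days prior to initiating protocol therapy".

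**Where it is barred.** Appendix E 3.7.2 says: "Treatment and other protocol-specific interventions may not be initiated until the Participating Institution receives confirmation of the participant's registration from the Coordinating Center". It also requires that the sponsor and the DFCI IRB be told of breaches. Appendix E 2.3 lists among the duties of participating institutions: "Register participants through the Coordinating Center prior to beginning research related activities". Section 12.3 commits the protocol to Appendix E.

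**Registration rules.** Section 4.1 asks DF/HCC institutions only to register before protocol therapy. Section 4.3 tells other sites: "Following registration, participants should begin protocol therapy within 7 days". It refers issues that would delay treatment to the Overall PI.

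**The concern.** An external site that follows the calendar and takes the biopsy during screening acts as Section 9 permits and as Appendix E 3.7.2 forbids. A DF/HCC site doing the same thing meets no such bar in Section 4.1.

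Two things are at stake. The first concerns patients. Screening comes before eligibility is confirmed, so someone can have an invasive research procedure and then prove ineligible. Appendix B lists major bleeding, transfusion, hospitalization and damage to adjacent organs among the less likely risks of core biopsy. Such a patient would bear those risks for a sample that cannot enter the paired or response analyses. The second concerns conduct: sites and monitors have no single text that tells them whether a screening biopsy must be reported.

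**Working it through.** No formula or stated figure underlies the timing rules, so the check compares the texts. The only arithmetic is the bound in step 5.

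1. **Does the Section 9 permission cover the biopsy?** Yes. The fresh-tissue row carries the same asterisk as blood and stool: "Baseline* (within 28 days of C1D1, prior to treatment start").

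2. **Does the Appendix E bar cover it?** On its wording, yes. The biopsy is a research procedure, not an eligibility test: criterion 3.1.5 requires agreement to undergo it, and Section 9.5 rests eligibility on local test results. Section 3.7.2 names treatment and, separately, other protocol-specific interventions, so it cannot be confined to drug administration.

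3. **Is there an exemption or an order of precedence?** Neither was found in Sections 4, 9, 10 and 12.3 or in Appendix E.

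4. **Does the sample logistics fit a screening biopsy?** Not at external sites. Section 9.2.3 requires cores to be labelled with the Study ID, and requires external sites to e-mail that ID the day before collection. Section 4.4 sends the study number together with the registration confirmation. Appendix E 3.8 assigns the case number only once eligibility is established and the participant is registered. The documents use three names for the identifier, but the Section 9 footnote itself links assignment of the study ID to the post-registration timing. A core taken before registration therefore cannot be labelled or announced as written.

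5. **How many patients could be biopsied and never treated?** The documents give no screen-failure rate. Assume a fraction f of 10% to 30%, with 30 patients treated (Section 13.1) and every biopsy done before the failing item is known. Number screened = 30 / (1 − f); failures = screened − 30.
   - f = 0.10: 30 / 0.90 = 33.3 screened, about 3 failures.
   - f = 0.30: 30 / 0.70 = 42.9 screened, about 13 failures.

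   Not every patient has an accessible tumor. Section 13.4 considers 15 or 20 paired biopsies from 30 patients, that is 0.50 to 0.67. With that as a rough proxy, the range becomes 3.3 × 0.50 ≈ 2 to 12.9 × 0.67 ≈ 9. Both ranges are ceilings.

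6. **What does this not touch?** Objective response is assessed among all patients who start protocol therapy (Sections 13.3 and 13.6.1), and the two-stage rule in Section 13.2 does not depend on biopsy timing. Sections 9.1 and 9.5 supply archival tissue for the central test where no baseline biopsy was done, and do not repeat earlier Foundation One testing. What a missed baseline biopsy would cost is fresh-tissue data, mainly the PD-L1 pair. The Section 13.4 table shows the sensitivity: for a 20% increase in positivity, power is 64% with 20 pairs and 54% with 15.

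**The case against.** The best defence is that the trial-specific footnote governs a generic appendix. Appendix E calls itself a reference for external sites. Its Section 3.8.2 defines a violation as a departure from the protocol without prospective IRB approval, and an act the protocol expressly permits is arguably no departure. Section 3.7.2 is headed as being about therapy. The line in Appendix E 2.3 is weak support: it stands in a list of duties that may apply, and read literally it sits badly with the screening results that Section 4.4 requires before registration. The protocol also already steers sites to post-registration timing, and it protects patients through signed consent in the registration packet, separate procedure consent, the safe-accessibility condition and a bar on general anesthesia.

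Much of this stands, and it rules out several stronger readings that a reader might infer:

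- **That one act is demonstrably compliant at one site and a violation at another.** The texts conflict, but the documents do not settle how a screening biopsy would be classed.
- **That external sites have a hard limit of 7 days.** Section 4.3 says participants should start in that time and sends delays to the Overall PI. A biopsy on Cycle 1 Day 1 before dosing is also allowed.
- **That the central mutational burden sample would be lost.** Archival tissue largely covers it.
- **That 3 to 13 patients would be harmed or biopsied needlessly.** That is an assumed ceiling, and nothing directs sites to biopsy before the other checks.
- **That consent is missing.** Consent can precede a screening biopsy. The gap is in registration and confirmed eligibility.

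The defence does not remove the contradiction. No rule of precedence is stated, Section 12.3 binds the trial to Appendix E, and the Study ID requirements in Section 9.2.3 fit only the post-registration timing.

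**Conclusion.** The point holds for external sites. Section 9 and the calendar permit a baseline research biopsy that Appendix E 3.7.2 bars before confirmed registration, and the labelling rules cannot be met at that stage. DF/HCC sites face no equivalent bar in Section 4.1.

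The effect is on trial conduct and on patients who fail screening. The number affected is unknown, and the bound in the working depends wholly on the assumed failure rate and on every biopsy coming first. Sample size, error rates, the response analysis and its population do not change. Because the biopsy result plays no part in eligibility, the exposure is avoidable at little cost, which makes the correction worth making although the issue is modest.

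**What to change.** Reconcile the Section 9 footnote, Section 9.2.2, the Section 10 calendar with footnote m, and Appendix E 3.7.2 into one rule for all sites:

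- Make the stated preference the requirement for the biopsy: after every other eligibility item is documented and registration is confirmed, and before the first dose. Move the calendar entry out of the Screening column accordingly.
- Keep the footnote's permission for baseline blood and stool only, and exempt those samples in Appendix E 3.7.2 when taken under signed consent.
- State in Section 4.3 that scheduling the biopsy is an accepted reason to go beyond the 7 days.

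One exempting sentence for all baseline samples in Appendix E would also end the conflict with Section 3.7.2. It would leave patients open to biopsy before eligibility is known, and would leave the Study ID problem in place.

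The cost is protocol and calendar wording, and a possible delay of a few days to the first dose at some sites.

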### 9.1 Archival Tissue

Archival tissue will be obtained on all participants. One block or 10-20 5 micron unstained, charged slides will be collected to centrally test for hypermutation status for participants that are unable to undergo a baseline biopsy. Local tests will be used for eligibility and if the participant had prior Foundation One testing, it will not need to be centrally repeated. Any leftover tissue or tissue from participants who had a baseline biopsy will be banked and stored for future research as a part of correlatives for this clinical trial or otherwise.

## 9.2 Fresh Tissue Biopsy

### 9.2.1 Objectives:

- Characterizing immune markers in hypermutated HER2- metastatic breast cancer
- To evaluate MET and phospho MET expression in tumor tissue at baseline by immunohistochemistry

### 9.2.2 Collection

Biopsies will be performed at the below timepoints, if tumor is safely accessible.

Mandatory:

- Baseline (preferably after registration or on Cycle 1 Day 1 prior to dosing):
- Around C1D29 (Any time from C1D29-C2D1 is allowed)

Optional:

- At time of progression or end of treatment

For patients proceeding to the retreatment phase, optional biopsies will be performed at the below timepoints:

- C1D1 of retreatment, prior to dosing
- At the time of progression after retreatment with nivolumab

Biopsies should not be performed on Friday afternoons, as there may not be time for processing of the fresh tissue. If a biopsy must be performed on Friday morning, the lab of [name] and [name] must be notified ahead of time to ensure that there will be adequate time for processing fresh tissue, since fresh tissue cannot be stored over the weekend. The specimens in RNALater, OCT, and formalin may be stored over the weekend and shipped on Monday. Specimens in RNA Later and formalin should be stored at room temperature until shipment.

